7.8.2 PK Analysis

Plasma concentration of IW-1973 will be summarized using the PK Population for each assessment timepoint by active treatment groups. Concentrations that are below the limit of quantitation (BLQ) concentrations will be treated as zero for the computation of descriptive statistics. A by-subject listing of all concentration-time data for each treatment and scheduled sample collection time will be presented. A listing of PK blood sample collection times, and elapsed time relative to dose will be provided.

PK parameters will be summarized by treatment group using the PK Population. A by-subject listing of all PK parameters for each treatment and study day will be presented.

Changes to protocol procedures or events which may impact the quality of the PK data or alter the evaluation of the PK will be reviewed on a case-by case basis to determine if PK data

collected during the affected treatment period may be excluded from relevant PK summaries. Examples include, but may not be limited to, vomiting following oral dosing occurring within the time frame of 2 times the median time to maximum concentration (T_{max}), sample processing errors that lead to inaccurate bioanalytical results, missed doses and/or inaccurate dosing on or in relationship to the day of PK sampling. Deviations to procedures or events which do not impact the quality of the PK data such as a missed blood sample or deviations from blood collection times will not be considered for exclusion from PK summaries.

7.8.3 Graphical Presentation of PK Data

Geometric mean plasma concentrations will be plotted over time by treatment group on both a linear and a semi-logarithmic scale. Individual drug plasma concentrations will also be plotted over time. Geometric mean trough concentrations will be plotted over time by treatment group and scheduled time on both linear and semi-logarithmic scales. Both morning and evening troughs will be included in the graphic presentation. In the case of an apparent diurnal difference between morning and evening trough concentration, a separate presentation including only the morning trough concentration may be prepared. Individual drug trough plasma concentrations will also be plotted over time.

Scatterplots of individual C_{max} , AUC_{tau} , C_{trough} , and T_{max} values will be presented by treatment group for the PK population, with means and medians also presented on these graphs when possible.

7.8.4 PK-PD Analysis

To assess potential relationships between IW-1973 plasma concentrations and PD assessments, mean plots of change from time-matched baseline in 30-minute averages of ambulatory blood pressure and pulse assessments and mean plots of IW-1973 plasma concentration will be presented by treatment group for the PK population.

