2. STUDY OBJECTIVES

The objectives of the study are to compare the safety, tolerability, PK profile, and PD effects of 2 treatment regimens of IW-1973 Tablet (40 mg per day) administered orally for 2 weeks to patients with stable type 2 diabetes mellitus and hypertension.

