3.2 TREATMENTS ADMINISTERED

Patients will be randomized in a 5:5:3 ratio to 1 of 2 IW-1973 treatment regimens or placebo (all regimens will be masked) as outlined in [Table 1](#).

Table 1. Treatment Arm Dosing Regimens

Treatment Arm	Dose time	Days 1 to 7	Days 8 to 14
PBO/PBO	AM	Placebo (8 x placebo tablet)	Placebo (8 x placebo tablet)
	PM	Placebo (8 x placebo tablet)	Placebo (8 x placebo tablet)
BID/QD	AM	20 mg IW-1973 (4 x IW-1973 Tablet*) (4 x placebo tablet)	40 mg IW-1973 (8 x IW-1973 Tablet*)
	PM	20 mg IW-1973 (4 x IW-1973 Tablet*) (4 x placebo tablet)	Placebo (8 x placebo tablet)
QD/QD	AM	40 mg IW-1973 (8 x IW-1973 Tablet*)	40 mg IW-1973 (8 x IW-1973 Tablet*)
	PM	Placebo (8 x placebo tablet)	Placebo (8 x placebo tablet)

PBO = Placebo, BID = twice daily, QD = once daily

* All IW-1973 tablets are 5 mg oral tablets

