7. ANALYSIS METHODS

7.1 ANALYSIS POPULATIONS

The following analysis populations will be defined for the study:

Safety Population: The Safety Population will consist of all patients who received at least 1 dose of study drug and will be grouped according to actual study drug taken. All safety and tolerability assessments will be performed using the Safety Population.

PD Population: The PD Population will consist of all patients who received at least 1 dose of study drug and had at least 1 postdose PD assessment. All analyses of PD data will be performed using the PD Population.

PK Population: The PK Population will consist of all patients who received at least 1 dose of IW-1973 and had at least 1 postdose PK parameter assessment without events or deviations affecting the PK results. All analyses of PK data will be performed using the PK Population.

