7.8 PHARMACOKINETIC (PK) ANALYSIS

7.8.1 PK Parameters

The PK parameters listed in [Table 3](#) will be calculated for each patient, whenever possible, if systemic levels of IW-1973 are quantifiable. PK parameter calculations will be performed using noncompartmental methods with Phoenix® WinNonlin® Version 6.4, or higher, (Certara L.P., Princeton, New Jersey, United States).

Plasma concentrations that are below the lower level of quantification (LLQ) or missing will be treated as described in [Section 9.7](#) for the calculation of PK parameters. Actual sampling times relative to IW-1973 dosing times will be used in calculations of the PK parameters. Area under the concentration-time curve will be calculated by linear up/log down trapezoidal summation.

Table 3. PK Parameters

Parameter	Description
	To be calculated on Day 1 relative to the morning dose, unless otherwise noted
AUC _{last}	Area under the plasma concentration time curve from time zero to T _{last} , the time at which the last measurable plasma concentration (C _{last}) is observed.
AUC _{tau}	Area under the plasma concentration-time curve during a dosing interval (tau: 24 hours for QD regimen, 12 hours for BID). Actual elapsed time at tau will be used for the calculation. If the IW-1973 sample at the end of the dosing interval is missing, AUC _{tau} will not be determined. If the IW-1973 sample at the end of the dosing interval is BLQ, AUC _{all} will be used to describe AUC _{tau} . For the BID regimen, this parameter will be calculated for the morning and for the evening dose, and for the 24-hour sampling period on Day 1 (AUC ₂₄).
AUC _{tau} /D	Dose-normalized AUC _{tau} . For the BID regimen, this parameter will be calculated for the morning dose and overall for the 24-hour sampling period (AUC ₂₄).
T _{max}	Time of maximum observed plasma concentration, obtained directly from the concentration-time profile. For the BID regimen, this parameter will be calculated for the morning and for the evening dose.
C _{max}	Maximum observed plasma concentration, occurring at T _{max} . For the BID regimen, this parameter will be obtained from the observed concentration-time data for the morning and for the evening dose as well as overall (C _{max,24}) for the 24-hour sampling period.
C _{max} /D	Dose-normalized C _{max}

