AUC_{last}	Area under the plasma concentration time curve from time zero to T_{last} , the time at which the last measurable plasma concentration (C_{last}) is observed
C_{max}	Maximum observed plasma concentration, occurring at T_{max}
SC_{max}	Ratio of C_{max} obtained after switching to the 40 mg QD regimen on Day 8 divided by C_{max} following the morning 20 mg BID dose on Day 7 (BID/QD regimen)
C_{max}/D	Dose-normalized C_{max}
T_{max}	Time of maximum observed plasma concentration
To be calculated on Day 14	
AUC_{last}	Area under the plasma concentration time curve from time zero to T_{last} , the time at which the last measurable plasma concentration (C_{last}) is observed
AUC_{tau}	Area under the plasma concentration-time curve during a dosing interval (tau: 24 hours). Should either the predose or the 24-hour postdose sample be missing, the concentration of the other sample (eg, predose for missing 24 hour) will be substituted for calculation of AUC_{tau} .
AUC_{tau}/D	Dose-normalized AUC_{tau}
$RAUC_{tau}$	Accumulation ratio of AUC_{tau} comparing Day 14 with Day 1, calculated as 
 • QD/QD regimen: Day 14 AUC_{tau} / Day 1 AUC_{tau} • QD/BID regimen: Day 14 AUC_{tau} / Day 1 AUC_{24}
C_{max}	Maximum observed plasma concentration, occurring at T_{max}
RC_{max}	Accumulation ratio of C_{max} comparing Day 14 with Day 1 calculated for the QD/QD regimen only
C_{max}/D	Dose-normalized C_{max}

Table 3. PK Parameters

Parameter	Description
C_{trough}	Trough plasma concentration observed at the end of a dosing interval (collected before the next administration) and will be correspond to the following sample collection times: 
 • 24-hour trough following the QD dose on Day 13: Day 14 predose • 24-hour trough following the QD dose on Day 14: Day 14 24-hours postdose
RC_{trough}	Accumulation ratio for C_{trough} comparing the trough following the IW-1973 dose on Day 14 with the trough following the IW-1972 dose on Day 1, calculated as: Day 14 24-hour postdose concentration / Day 2 morning predose concentration. Note: for the BID regimen, this comparison is made relative to the trough following the evening dose on Day 1 (ie, following the total daily dose of 40 mg)
CL/F	Apparent total body clearance after oral administration, calculate as the administered dose divided by AUC_{tau} . No dose adjustment is required in this calculation.

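### SAP 7.8.4 looks for a concentration-BP relationship only through arm-mean curves, which carry no between-arm exposure contrast on Day 14 and never pair a patient's concentration with that patient's BP

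*SAP*

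**What the plan says.** SAP 7.8.4 is the only PK-PD analysis in the visible text. Its purpose is to look for relationships between plasma concentration and the PD measurements. The method is to present "mean plots of change from time-matched baseline in 30-minute averages of ambulatory blood pressure and pulse assessments and mean plots of IW-1973 plasma concentration", by treatment group, in the PK Population. It names no correlation, model or patient-level plot.

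SAP 7.1 limits that population to "all patients who received at least 1 dose of IW-1973 and had at least 1 postdose PK parameter assessment" (and without events that affect the PK results). Placebo patients, the only ones with zero exposure, are therefore outside the display.

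SAP 2 describes "2 treatment regimens of IW-1973 Tablet (40 mg per day) administered orally for 2 weeks". In SAP Table 1 the BID/QD arm takes 20 mg morning and evening on Days 1 to 7, while the QD/QD arm takes 40 mg in the morning. On Days 8 to 14 both arms take 40 mg in the morning. SAP Table 3 acknowledges the switch with a ratio built on the Cmax "obtained after switching to the 40 mg QD regimen on Day 8".

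Individual concentrations are listed (SAP 7.8.2) and plotted over time, and individual PK parameters are shown as scatterplots by arm (SAP 7.8.3). None of these is set against BP. SAP 7.7.2 and 7.7.3 separately give ABPM least squares means and differences from placebo with 95% intervals.

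**The concern.** A PK-PD display informs only to the extent that exposure varies in what it shows. Averaging within arm removes the variation between patients and leaves two sources: the difference between the arms, and the rise and fall of each arm's mean curve. The first vanishes once the regimens coincide. The second is tied to time since dose, and any delay between concentration and effect blurs it further.

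At stake is whether the trial can say anything quantitative about how BP tracks exposure. SAP 6.6 says the PK and PD analyses favour estimation over testing, and SAP 7.7.2 attaches intervals to most change-from-baseline PD endpoints. SAP 7.8.4 produces neither an estimate nor an interval, although the data for a patient-level look are already scheduled.

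**Working it through.** The documents give no PK-PD figure to reproduce. They also give no half-life, exposure CV or BP standard deviation, so those values below are assumptions shown as ranges.

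**1. Arms and dose.** 26 × 5/13 = 10 per active arm and 26 × 3/13 = 6 on placebo, so 20 active patients. "All IW-1973 tablets are 5 mg oral tablets", so QD is 8 × 5 = 40 mg and BID is (4 + 4) × 5 = 40 mg per day. The daily dose ratio is 1.00.

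**2. Pairs available.** Post-dose PK samples that fall within ABPM, in hours after the morning dose (Schedule of Events; Protocol 3.8.2):
- Day 1: 1, 3, 6, 12, 13, 15, 18, 24 (8 samples)
- Day 7: 1, 3, 6, 12, 24 (5 samples)
- Day 14: 1, 3, 6, 12, 24 (5 samples)

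8 + 5 + 5 = 18 per patient, and 18 × 20 = 360 if complete. Two arm means at each time give 18 × 2 = 36 points. The 24 h sample pairs with the last ABPM window (23.5 h in SAP Table 5).

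**3. Exposure contrast between arms.** One-compartment oral superposition: C(t) ∝ Σ D·ka/(ka − ke)·[exp(−ke·Δt) − exp(−ka·Δt)], with ke = ln 2 / half-life. Assumed half-life 6 to 48 h and ka 0.5 to 1.0 per h. QD/QD to BID/QD ratios:

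| Day | Cmax after AM dose | 24 h trough | AUC over 24 h |
|---|---|---|---|
| 1 | 2.00 | 0.40–0.92 | 1.13–1.34 |
| 7 | 1.09–1.55 | 0.40–0.91 | 1.00–1.01 |
| 14 | 0.99–1.00 | 0.99–1.00 | 0.99–1.00 |

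The contrast is absent on Day 14 and for Day 7 AUC. It is present on Day 1 and in Day 7 peaks and troughs. Within one arm, concentration over the sampled times on the three days varies about 3.6- to 11-fold (QD/QD) and 4- to 16-fold (BID/QD), and the mean curves do show this.

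**4. Variation averaged away.** P90/P10 of patient exposure = exp(2 × 1.2816 × √ln(1 + CV²)). This is 2.1 at CV 30% and 3.4 at CV 50% (both assumed).

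**5. What each level of data can estimate.** SE of the BP slope per doubling of exposure, one value per patient, with g = ln(arm ratio) and s² = ln(1 + CV²):
- arm means: SD·√(2/10)/g·ln 2
- patient level: SD/√(20(g/2)² + 18s²)·ln 2

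With SD 10 mmHg and CV 30%, and in brackets the range over SD 8–12 and CV 30–50%:

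| Arm ratio | Arm means, mmHg | Patient level, mmHg |
|---|---|---|
| 1.0 | not estimable | 5.6 (2.8–6.7) |
| 1.3 | 11.8 (9.5–14.2) | 5.0 (2.7–6.0) |
| 2.0 | 4.5 (3.6–5.4) | 3.5 (2.2–4.2) |

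**6. Limits of the patient-level look.** Smallest correlation with 80% power at two-sided 5%: tanh((1.960 + 0.842)/√(n − 3)).
- n = 20: tanh(2.802/4.123) = 0.59
- n = 26, placebo at zero exposure: tanh(2.802/4.796) = 0.53

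For an observed r of 0.5 at n = 20, 0.549 ± 1.96/4.123 on the Fisher scale gives a 95% interval of 0.07 to 0.77.

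**The case against.** A reader might infer more than the documents support, and four objections narrow the point.

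- **Equal daily dose does not mean no exposure contrast.** In Week 1 the morning dose differs two-fold by design, and peaks and troughs differ. The no-contrast statement holds for Day 14, not for the display as a whole.
- **The patient-level data are not thrown away.** SAP 7.8.2 and 7.8.3 list and plot individual concentrations. Only the pairing with BP is missing. Figure specifications sit in a separate document (SAP 1) that is not available here, so a patient-level plot could exist there. The SAP does not commit to one.
- **The mean curves are not simply confounded with clock time and meals.** BP enters as change from the same clock interval on Day -1, which already falls within confinement on the standard diet. SAP 7.7.2 and 7.7.3 also supply a placebo reference for ABPM. Drift over the stay is not removed inside the 7.8.4 display itself, because placebo is absent from it.
- **No stated objective is missed.** The objective in Protocol 2 and SAP 2 compares regimens. Inference is descriptive (SAP 6.1), and the sample size has no statistical basis (SAP 4).

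It can also be said that a model on the 360 pairs would be no cleaner, since part of its slope comes from the within-day rise and fall. That is fair against a model with only concentration and day. It is why any slope should also carry placebo and nominal postdose time. It does not count against simple scatterplots, or against relating a patient's 24-hour BP change to that patient's own AUC.

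**Conclusion.** The point holds in limited form and is minor. SAP 7.8.4 asks about a relationship and plans only arm-mean curves in IW-1973-treated patients. On Day 14 those curves have no between-arm exposure contrast, so a between-arm slope cannot be estimated. At an arm ratio of 1.3, near the top of the modelled Day 1 AUC range, its SE would be roughly 9.5 to 14 mmHg per doubling, against 2.7 to 6.0 at patient level. Variation between patients, about 2- to 3-fold under the assumed CVs, goes unused.

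The mean overlays still have value for timing and possible delay. The gain from patient-level displays is real but modest, since 20 active patients resolve only correlations near 0.6. The dose identity and pair count rest on the documents (the count assumes complete data). The exposure ratios, CVs and SEs rest on the stated assumptions.

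**What to change.** Keep the mean plots in SAP 7.8.4 and add the following, labelled exploratory and descriptive.

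(a) For each of Days 1, 7 and 14, a patient-level scatter of the 30-minute ABPM change (from the same clock time on Day -1) against the concurrent concentration, with placebo patients shown at zero. If a slope with 95% interval is reported, take it from a repeated-measures model that includes placebo, day and nominal postdose time. Because placebo is included, state that the slope partly reflects the drug-placebo difference.

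(b) A scatter of change in 24-hour average systolic BP and pulse against the patient's own 24-hour AUC on Days 1 and 14. Day 7 is left out because SAP Table 3 uses a 12-hour interval for the BID arm that day.

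Name the analysis set, since the SAP's PK Population excludes placebo. Make the change before unblinding, the deadline that Protocol 3.9 sets for the SAP.

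Cost: SAP wording and a small amount of programming, with no added samples or visits. "Actual sampling times relative to IW-1973 dosing times will be used in calculations of the PK parameters", so the times needed for matching are already held. Downside: a few extra exploratory outputs with wide intervals. A lag between concentration and effect would limit how (a) can be read.

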7.9 SAFETY ANALYSIS

All safety analyses will be performed using the Safety Population.

7.9.1 Adverse Events

All adverse events (AEs) will be coded using the Medical Dictionary for Regulatory Activities (MedDRA) Version 19.1 and will be classified by MedDRA system organ class (SOC), and preferred term (PT).

Treatment-emergent adverse events (TEAEs) are those AEs that started or worsened in severity after the administration of study drug. If it is not possible to determine when the event started due to incomplete start dates/times, it will be assumed to be treatment-emergent.

The number and percentage of patients who experience at least one TEAE as well as those who experience each specific SOC and PT will be presented by treatment group as well as for IW-1973 overall using the Safety Population. TEAEs will also be summarized by week, where TEAEs that started during Week 1 (study days 1-7) or Week 2 (study days 8-14) will be presented by treatment group for the respective week. Summaries of study drug-related TEAEs will also be presented by treatment group. For presentation of AE incidence, AEs will be sorted alphabetically by SOC, and within each SOC, by decreasing incidence of PT in the overall group.

In addition, AEs in screen failure patients, TEAEs, severe TEAEs, study drug-related AEs (those that are determined by the Investigator to be related to study drug), serious AEs, AEs that resulted in study discontinuation, and AEs that resulted in death (if any) will be presented in separate listings.

Adverse Events of Clinical Interest

Since an increased risk for bleeding may represent a class effect with sGC stimulators, bleeding events and TEAEs related to bleeding will be summarized by treatment group and presented in a data listing. Similarly, TEAEs associated with hypotension or lowering of BP will be summarized by treatment group and presented in a data listing. See [Appendix 1](#) for details on the determination of the events for each category of interest.

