3.2 DISCUSSION OF STUDY DESIGN INCLUDING THE CHOICE OF CONTROL GROUPS

A double-blind, placebo-controlled, randomized study design was chosen to investigate the safety PK, PD, and tolerability of 2 daily 40-mg IW-1973 dosing regimens. Patients will be randomized to ensure that the treatment groups are comparable and to minimize the potential for selection bias. The study will be double blind and treatments will be masked to ensure that the subjects and clinic staff are unaware of the dosing assignment and to minimize potential for bias in study assessments or in reporting of AEs. Placebo was chosen as the control so that the rate of spontaneously occurring AEs can be determined and to reduce the potential for bias in the reporting of AEs. Randomization will occur so that, within a particular cohort, an optimal number of subjects can be exposed to a particular dose of IW-1973, while at the same time ensuring that a reasonable number of subjects across the cohorts receive placebo for AE and PD comparisons. This design is in accordance with the concepts in International Conference on Harmonisation (ICH) E10, Choice of Control Groups and Related Issues in Clinical Trials (International Conference on Harmonisation of Technical Requirements for Registration of Pharmaceuticals for Human Use, 2001).

Patients will be confined to the Study Center for the full duration of dosing through 24 hours after the final dose to allow monitoring of safety parameters and assessment of any PD effects of IW-1973. In addition, Stopping Criteria (Section [3.6](#)) have been established to ensure that dosing will stop should a safety signal be detected. Patients will have a Follow-up Visit 7 (\pm 2) days after the final dose of study drug and an End of Trial Visit 28 (\pm 3) days after the final dose to determine if any AEs have developed and if any AEs that were ongoing at the time of Discharge have resolved.

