3.5.4 Selection and Timing of Dose for Each Patient

All patients will receive 2 orally administered doses per day: an AM dose and a PM dose. Except for Day 13, patients will receive the AM dose at approximately the same time (\pm 15 minutes) every day in the morning (8 to 10AM) following an overnight fast of \geq 8 hours. (Note: For each patient, the first dose on Day 1 may be administered between 8 and 10AM; thereafter, AM doses on Days 2 to 12 and on Day 14 must be administered within 15 minutes of the time of dosing on Day 1.) On Day 13, first dose should be administered in the morning between 7 and 10:30AM,

after the EndoPAT assessment (when applicable). Breakfast should begin within 30 minutes after dosing. Each patient will receive their PM dose 12 hours (\pm 30 minutes) after their AM dose and at least 30 minutes after completing a normal dinner.

Patients may take multiple tablets together. Permitted concomitant may be taken at the same time as study drug.

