3.7.3.9 Recording Adverse Events

Adverse events will be collected and recorded from the time the patient signs the ICF at the Screening Visit through the End of Trial Visit. All AEs, regardless of the assumption of a causal relationship with study procedures or study medication, must be recorded in the patient's source documentation and subsequently on the appropriate AE page of the patient's eCRF. This record includes AEs the patient reports spontaneously, those observed by the Investigator, and those elicited by the Investigator in response to open-ended questions during the study, such as "Have you had any health problems since your last visit?"

For every AE, the Investigator must

- Provide an assessment of the severity, causal relationship to the study medication, and seriousness of the event
- Document all actions taken with regard to the study medication (ie, no action taken, treatment temporarily interrupted, or treatment discontinued)
- Detail any other treatment measures taken for the AE, including concomitant medications and/or procedures

Pretreatment AEs will be collected from the time the patient signs the ICF until the patient receives study drug. Pretreatment AEs will be captured in the patient's source documentation but will only be entered for patients who receive study drug on the AE page of the patient's eCRF.

Laboratory abnormalities and changes in vital signs, physical examination findings, and 12-lead ECG parameters should be considered AEs and reported on the AE page of the patient's eCRF if the Investigator considers them clinically significant and/or they necessitate intervention.

Any medical condition that is present when a patient is screened and does not worsen in severity and/or frequency should be reported as Medical History and not as an AE. However, if the condition does deteriorate in severity and/or frequency at any time during the study, it should be reported as an AE.

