3.8.2.11 Discharge (Day 15)

- Weight

- Respiratory rate and oral temperature
- ABPM ends 12 hours (\pm 15 minutes) postdose
- 12-lead ECG
- Supine BP (average of 3 measurements) and pulse at 12 hours (\pm 15 minutes) postdose
- Supine-to-standing (orthostatic) pulse and BP at 12 hours (\pm 15 minutes) postdose
- Physical examination
- Collection of blood at 12 hours (\pm 15 minutes) postdose:
 - PK
 - Clinical chemistry, hematology (CBC), coagulation
 - Hemoglobin A1c
 - Fasting plasma glucose
 - Fasting plasma insulin
 - [REDACTED]
- Collection of urine samples, first void
 - Urinalysis
 - Urine albumin and creatinine
- AE evaluation
- Concomitant medication recording
- Discharge from the clinic

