3.9.3.4 Safety Analyses

3.9.3.4.1 Adverse Events

Adverse events will be coded using the latest version of Medical Dictionary for Regulatory Activities (MedDRA) available at the start of the study. Treatment-emergent adverse events (TEAEs) are those AEs that started or worsened in severity after the administration of study drug. All TEAEs as well as those that occurred during the first 7 days of treatment will be summarized by system organ class (SOC) and preferred term (PT) for each treatment group. In addition, listings of severe TEAEs, drug-related TEAEs, SAEs, AEs leading to study discontinuation, and AEs leading to death (if any) will be provided.

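### The by-week TEAE summary is cut on undefined study days, so on a calendar reading TEAEs before the Day 8 switch dose count in the QD week and TEAEs from Day 15 onward fall in neither week

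*SAP*

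**What the plan says.** SAP 7.9.1 assigns events to weeks by when they started: "TEAEs that started during Week 1 (study days 1-7) or Week 2 (study days 8-14) will be presented by treatment group for the respective week". It gives no dose time as the boundary, and study day is not defined anywhere in the SAP. The TEAE definition has no upper time limit: "Treatment-emergent adverse events (TEAEs) are those AEs that started or worsened in severity after the administration of study drug". Protocol 3.9.3.4.1 planned an early-period summary only, in which "those that occurred during the first 7 days of treatment will be summarized by system organ class". SAP Section 8, which lists changes from the protocol, does not mention the by-week windows.

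The BID/QD arm changes regimen at the Day 8 AM dose (Protocol Table 2, SAP Table 1). Protocol 3.5.4 puts the Day 1 AM dose between 8 and 10 AM and adds that "AM doses on Days 2 to 12 and on Day 14 must be administered within 15 minutes of the time of dosing on Day 1".

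Observation runs past Day 14. Protocol 3.2 states: "Patients will be confined to the Study Center for the full duration of dosing through 24 hours after the final dose". The Day 15 list in Protocol 3.8.2.11 includes "Clinical chemistry, hematology (CBC), coagulation", together with urinalysis, an ECG, a physical examination and supine-to-standing blood pressure. Under Protocol 3.7.3.9, laboratory, vital sign, examination and ECG abnormalities "should be considered AEs and reported on the AE page of the patient's eCRF if the Investigator considers them clinically significant". AE collection continues to the End of Trial Visit on Day 42 (±3).

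**The concern.** One declared purpose of the trial (Protocol 1.1) is to see whether starting with a week of BID dosing makes 40 mg per day easier to tolerate. The by-week TEAE summary is the only AE incidence summary that separates that week from the QD week that follows. If its boundary is midnight, it does not match the switch. A BID/QD patient who becomes dizzy in the predose supine-to-standing test on the morning of Day 8 has had BID dosing only, yet the event is tabulated with the QD week.

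At the other end, a clinically significant finding first seen in the Day 15 laboratory tests, ECG or examination, and dated that day, has no column. Nor does anything that starts during follow-up. A reader of the by-week table alone would not know that these events exist.

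**Working it through.** The plan states no figure for this point, so there is none to reproduce. The check is clock arithmetic.

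**Inputs**
- AM dose clock time *t*: 8 to 10 h after midnight; 7.75 to 10.25 h on Day 8 with the 15-minute tolerance (Protocol 3.5.4).
- PM dose: nominally *t* + 12 h, ±30 minutes (Protocol 3.5.4).
- Day 15 assessments: 12 h ±15 minutes after the Day 14 PM dose (Protocol 3.8.2.11).
- Arm sizes: 26 patients at 5:5:3, so 26 × 5/13 = 10, 10, and 26 × 3/13 = 6.

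**Which reading of study day?** Protocol 3.8.2.4 lists the PK sample taken 6 h after the Day 1 PM dose under Day 2. With a PM dose at 8 to 10 PM, that sample falls at 2 to 4 AM, before the Day 2 AM dose. The Day 8 predose assessments are likewise listed under Day 8. Both fit calendar labelling.

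**Results on the calendar reading** (nominal times)

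| Quantity | Formula | Result |
|---|---|---|
| Day 8 predose time counted in Week 2 | *t* | 8 to 10 h |
| Share of a 168 h week | *t*/168 | 4.8 to 6.0% |
| Same, with the 15-minute tolerance | 7.75/168 to 10.25/168 | 4.6 to 6.1% |
| Total over 10 BID/QD patients | 10*t* | 80 to 100 patient-hours |
| On-treatment time in Week 1 | 168 − *t* | 158 to 160 h |
| Time after the Day 14 AM dose kept in Week 2 | 24 − *t* | 14 to 16 h |
| Day 15 assessments, time past the end of Week 2 | *t* + 12 + 12 − 24 | 8 to 10 h |
| Days in neither week, to nominal Day 42 | 42 − 15 + 1 | 28 of 42 |

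**How the SAP treats the same hours elsewhere**
- PK (SAP Table 3): the Day 8 predose concentration is the trough of the Day 7 dosing, and the 24 h sample is the trough of the Day 14 dose.
- ABPM (SAP 7.7.1 and Table 5): a postdose day runs from one AM dose to the next, so the Day 7 recording ends at dosing on Day 8.

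The early hours of Day 8 therefore belong to Day 7 for PK and ABPM but, on the calendar reading, to Week 2 for TEAEs.

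**Effect on a table row.** SAP 9.2 counts each patient once per SOC, PT or overall. Moving one event changes a week's rate by 1/10 = 10 points only if that patient has no other event for the row in that week. Both weeks change by 10 points only if there is no other such event in either.

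**End of Week 2.** With the PM dose and assessment tolerances, the Day 15 assessments fall 24 h ±0.75 h after the Day 14 AM dose (23.25 to 24.75 h). A purely dose-anchored Week 2 ending at 24 h would split them, so the end needs its own rule.

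**The case against.** The strongest reply is that the calendar cut is inferred. SAP Table 1 uses Days 1 to 7 and Days 8 to 14 as dosing columns, the protocol speaks of days of treatment, and the table specifications are in a separate document (SAP Section 1) that may define the term. This stands: the Day 8 part depends on a reading that the SAP leaves open. It does not remove the need for a definition, and an end rule for Week 2 is needed on either reading.

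Four stronger readings are tempting, and the documents do not support them.
- *The by-week table is the only display separating the regimens.* PD results and vital signs are also summarised by timepoint (SAP 7.7.2, 7.9.5) and PK by day (Table 3). Only for AE incidence is it the sole summary.
- *Day 15 findings are lost.* They remain in the overall TEAE table and the listings. Day 15 also has its own laboratory shift tables, ECG shift table and physical examination listing (SAP 7.9.2, 7.9.6, 7.9.6.2).
- *The cut biases BID/QD against QD/QD in Week 1.* A midnight cut takes the same 8 to 10 h from every arm, so observation time in that contrast stays balanced. What changes is the regimen label in BID/QD, in a comparison across weeks that is confounded with time on drug wherever the cut is placed.
- *Day 15 belongs in Week 2.* Week 1 ends with no equivalent laboratory, ECG and examination battery. Merging Day 15 into Week 2 would make ascertainment unequal between the weeks, and an abnormality that arose in Week 1 could be found on Day 15 and charged to Week 2.

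It is also fair to say that the safety analyses are descriptive, that no decision rule uses this table, and that with 26 patients a boundary event can be looked up in the listings.

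**Conclusion.** The concern holds as a modest defect in an analysis definition. On the calendar reading, 8 to 10 h per patient (4.8 to 6.0% of a 168 h week) that follow only BID dosing in the BID/QD arm count in the QD week, which is inconsistent with the SAP's own PK and ABPM conventions. TEAEs starting on Day 15 or later have no by-week column. An event found on Day 15 but dated Day 14 would still be in Week 2.

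The size in hours equals the size in events only if the event rate is constant over the week, which is an assumption; the documents give no event rates. The 10-point figure is an upper limit per row and week, for one patient with all 10 in the arm counted. The change is worth making because it costs little and concerns the one AE summary aimed at the BID-week question.

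**What to change.** In SAP 7.9.1, replace the study-day windows with dose-anchored ones.
- **Week 1:** first dose to just before the Day 8 AM dose. State how the period ends for a patient who stops before Day 8.
- **Week 2:** Day 8 AM dose to 24 h after the last AM dose.
- **Post-treatment:** a separate column for TEAEs first identified at the Day 15 discharge assessments or later. Let this rule take precedence over the 24 h bound, since those assessments can fall up to 0.75 h before it.
- **Day 8 events without a start time:** one fixed assignment rule, with the number of such events in a footnote.
- **Denominator:** patients dosed in the period, for Week 1 and Week 2 each.

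Add the change to SAP Section 8. The cost is SAP wording and slight extra table programming, with no change to trial conduct. The fix relies on AE start times. SAP 7.9.1 and 9.3 imply that these are recorded, since both refer to incomplete start dates and times, but Protocol 3.7.3.9 does not require them explicitly. Confirm this against the eCRF.
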